4.0 Study Intervention(s)/Interaction(s)

Care to Plan (CtP) is an online care planning tool that provides a succinct and clear overview of various types of ADRD caregiver interventions, administers a brief validated assessment of risk, and generates individualized service recommendations for Alzheimer's disease and related dementia (ADRD) caregivers as well as resources that link users to a selected recommendation. Caregivers will complete the tool with the guidance of a CtP interventionist (Senior Care Navigator/Riverside Health System staff).

PROTOCOL TITLE: Care to Plan: Preliminary Efficacy of a Tailored Resource for Family Members of Persons with Dementia

The interventionist will discuss CtP recommendations with caregivers and help caregivers enroll in a recommended support service if so desired. The online tool is located at: <https://caretoplan.ahc.umn.edu/>. Following completion of CtP assessment and consultation, participants would receive a mailing (or e-mailing) including the recommendations generated by the tool.

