The qualitative and quantitative data available from Phase I will be employed to refine the content and delivery of CtP prior to phase II. In phase II, 100 caregivers of persons with ADRD will be enrolled. Similar to phase I, after receiving a new

PROTOCOL TITLE: Care to Plan: Preliminary Efficacy of a Tailored Resource for Family Members of Persons with Dementia

contact, the UMN team will conduct a telephone-based screening for eligibility, complete consent, and administer the baseline survey. Participants will be randomly assigned in a 1:1 ratio to receive either the CtP intervention or a usual care control condition. The UMN team will generate a random assignment schedule using <http://randomizer.org>. The research staff who will have responsibility for all follow-up data collection will not have access to the random assignment schedule, nor will they be able to determine the next treatment assignment in the sequence. The randomization procedures will ensure both random assignment as well as treatment concealment during data collection and are consistent with CONSORT recommendations. Participants in both groups will be followed for six months with data collection at baseline, three months, and six months. For Phase II, a brief disposition survey to determine the participant's caregiving status, as well as the status of the person they provide care for, will be administered (at 3 and 6 month follow up) prior to administering the appropriate survey. An embedded experimental mixed methods design will be utilized ([QUAN+qual]→qual) that will incorporate various qualitative data collection elements within and following the 6-month randomized controlled evaluation of CtP.

As of February 2021, only those with an ID number (i.e. those reviewing the tool with study interventionists) will have their CaretoPlan responses tracked. Thus, others using the tool for personal use within or outside of the context of the study will no longer have responses tracked. *Note: If it is learned that someone enrolled in the study reviewed the tool on their own prior to reviewing it with a study interventionist, this information will be tracked internally.*

As with phase I, surveys will be administered via telephone or in hard-copy surveys.

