Caregivers of persons with memory loss who contact RHS Senior Care Navigation or other RHS services will likely seek information and support. Senior Care Navigators, social workers, or similar staff will deliver routine care and services to caregivers regardless of: a) whether they decide to enroll in the CtP project; or b) if they are randomly assigned to the control condition. Participants assigned to the usual care control group will be provided with the contact information for Senior Care Navigation. These participants may contact Senior Care Navigation for information and support as desired. Care to Plan enhances standard RHS care by creating a more structured assessment process along with individually tailored recommendations, thus resulting in a more efficient referral process. The time spent using the electronic CtP tool will be tracked. Given the size of the proposed Phase II sample and the number of Care to Plan (CtP) interventionists ($n = 3$), a cluster randomization approach is not feasible. Based on Riverside Health standard practices, individuals may contact Riverside's SCN program for consultation as needed. SCNs will document contact with study participants in both the treatment and usual care groups. Comparisons across treatment and control conditions in the number of interactions with the interventionists (i.e., RHS Senior Care Navigators) will determine if alternative randomization approaches in subsequent, larger-scale evaluations of CtP are necessary.

As indicated in Phase I, a number of approaches will be adopted to examine the degree to which caregivers of persons with ADRD utilize CtP as well as their perceptions of acceptability of the online care planning tool. The time spent using CtP will be tracked, allowing for an analysis of practicality (i.e., how long caregivers actually utilize CtP). Those randomized to receive CtP will also be provided with access to the online tool following review of the tool with a Riverside Health care navigator.

For those completing CtP, the 21-item system review checklist will be administered at 3 to determine how well ADRD caregivers in the treatment group perceive CtP's performance, acceptability, and utility. For those in the treatment group who have not completed CtP by the 3 month time point, follow-up surveys will occur without administration of the review checklist.

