18.0 Confidentiality

18.1 Data Security: Please see above. No consent form will be placed in participants' medical, employment, or educational records.

Please note: [If there is interest in Care to Plan, the Riverside staff would complete the permission for contact form and securely share the contact information with the UMN research team]. Riverside Senior Care Navigators or other RHS staff may communicate/document about referrals made to Riverside Senior Care Navigation for consultation, interest/involvement in the Care to Plan study, and other referrals provided to individuals who may be enrolled in the Care to Plan study. This communication/documentation occurs outside of the study context (as a part of their routine roles in care consultation with Riverside Health System), and UMN study staff do not have access to the Riverside Epic electronic health record or to the staff's internal time tracking system where staff reference this information (SalesForce/Livwell).

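### Navigator contact counts alone do not measure contamination, yet they are the measure named for deciding the randomisation unit of later trials

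*Combined protocol and SAP*

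**What the plan says.** Section 5.1 explains that, given the planned sample and three interventionists, "a cluster randomization approach is not feasible", so caregivers are randomised individually. The question of a different unit is left to a later trial and tied to one measure: "Comparisons across treatment and control conditions in the number of interactions with the interventionists" "will determine if alternative randomization approaches in subsequent, larger-scale evaluations of CtP are necessary". No test, direction or threshold is given, and the protocol session is not excluded from the count.

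The two arms meet the navigators differently. In the CtP arm, "Caregivers will complete the tool with the guidance of a CtP interventionist" (section 4.0). In the control arm, "Participants assigned to the usual care control group will be provided with the contact information for Senior Care Navigation" (section 5.1), and calling is optional.

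On records, section 5.1 says "SCNs will document contact with study participants in both the treatment and usual care groups", without saying what is recorded about the content of a contact. It also says that from February 2021 "only those with an ID number (i.e. those reviewing the tool with study interventionists) will have their CaretoPlan responses tracked". Section 14.0 adds that the study team can reach those tool data through the Secure Computing Environment.

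**The concern.** The plan does not use the word contamination. However, comparing contacts with shared staff, directly after ruling out clusters, has little other purpose. The question for a later trial is how many controls received the intervention through those staff or found it themselves. A contact count answers a different question.

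- A difference between arms is expected even with no contamination, because one arm has a session built in.
- A difference, or its absence, says nothing about what was discussed when a control called.
- The count misses self-use. The tool is online, and eligibility requires willingness to use CtP (section 10.1), so controls know that it exists.

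At stake is a stated purpose of the trial. Section 17.2 says that Phase II is meant to generate power estimates for a larger evaluation. If some controls were exposed and nobody counted them, a small or null difference could not be attributed either to the tool or to dilution, and the diluted estimate would carry into the next design.

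**Working it through.** The plan gives no figure to reproduce and no contact rates. Every rate below is an assumption, used to show how the measure behaves.

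**Step 1. Inputs.** Section 5.1: 1:1 allocation of 100 caregivers. Section 17.2: 10% attrition at 6 months. Hence 100 × 0.9 / 2 = 45 per arm. Assumed: two-sided 5% level; routine contacts follow a Poisson distribution; one protocol session is added in the CtP arm unless stated.

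**Step 2. Does the comparison respond to exposure?** Contact counts were simulated 1,500 times per scenario and the arms compared by a Mann-Whitney test. Each control contact carried CtP content with a set probability. The cap is the expected share of controls with any contact, 1 − e^(−λ), where λ is the mean number of control contacts.

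| Mean routine contacts, control / CtP | Session counted | Controls exposed | Mean difference | Test significant | Cap |
|---|---|---|---|---|---|
| 1 / 1 | yes | 0% | 1.00 | 99.8% | 63.2% |
| 1 / 1 | yes | 39.6% | 1.00 | 99.9% | 63.2% |
| 1 / 1 | yes | 63.1% | 1.01 | 99.8% | 63.2% |
| 2 / 1 | yes | 0% | 0.00 | 6.7% | 86.5% |
| 2 / 1 | yes | 86.4% | −0.01 | 5.7% | 86.5% |
| 1 / 1 | no | 0% | 0.00 | 4.5% | 63.2% |
| 1 / 1 | no | 63.4% | 0.01 | 5.4% | 63.2% |

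Within each pair of contact rates the result stays the same while exposure runs from zero to the cap. This follows from the model, in which content does not alter the count. The table illustrates the logic and is not evidence about Riverside's calls. Excluding the session removes the built-in difference but does not make the comparison sensitive to exposure.

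**Step 3. What the count does show.** A control with no navigator contact cannot have received CtP from a navigator. If controls average 0.5 calls, the cap is 1 − e^(−0.5) = 39.3%. Exposure of 20% by that route would then need 0.20 / 0.393 = 51% of calling controls to have received CtP.

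**Step 4. Largest loss at a given exposure.** Assume a true effect of 0.6 SD, exposed controls gaining all of it, and a constant SD. With exposed share c, the observed effect is d = 0.6 × (1 − c), and power is about Φ(d × √(45/2) − 1.96).

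- c = 0: 0.60 × 4.743 − 1.96 = 0.886, power 81% (80% with the t distribution).
- c = 0.20: d = 0.48; 0.48 × 4.743 − 1.96 = 0.317, power 62%. The sample size needed rises by 1 / 0.8² = 1.56.

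A two-group comparison stands in here for the planned growth-curve model.

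**Step 5. Is a proportion usable at this size?** With 0 of 45 controls exposed, the upper 95% limit is 1 − 0.025^(1/45) = 7.9%. With 9 of 45 (20%), the Wilson interval has centre (0.2 + 3.84/90) / (1 + 3.84/45) = 0.224 and half-width 1.96 × √(0.16/45 + 3.84/(4 × 45²)) / (1 + 3.84/45) = 0.115, giving 10.9% to 33.8%. That is wide, but it bears directly on the question.

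**The case against.** The other side has a good case on several points.

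- **The count is informative.** A reader might infer that it can never lead to the right answer. That goes too far: a near-zero control count would largely rule out exposure through navigators, the route that matters most for shared staff. What it cannot do is place exposure between zero and the cap.
- **It is not the only relevant information.** A reader might call it the sole check on contamination. ID-linked tool records could show guided use by a control if an ID was entered. Section 17.1 explores degree of contact in both arms against outcomes and compares use of recommended services. The interventionists are interviewed. Section 5.1 also logs self-use if it is learned of, though that note is worded for use before a navigator review, which controls do not have during their six months. None of these is tied to the decision on randomisation unit.
- **There is no rule to be wrong.** The plan does not say that a large difference means good separation or a small one contamination. The missing direction and threshold are part of the problem.
- **Access to records.** A reader might take "UMN study staff do not have access to the Riverside Epic electronic health record" (section 18.1) to mean that the content of contacts is out of reach. That sentence concerns routine documentation outside the study; it does not say that the contact documentation promised in section 5.1 is unavailable.
- **Timing and reach.** Recruitment ended on 12/1/2021 and the current version is dated 4/28/23, so new data items probably cannot capture this cohort. The comparison also does not enter the primary analysis. Both points stand and limit the remedy to analysis and reporting here.

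**Conclusion.** The concern holds in a limited form. The measure named for the decision counts contacts, includes a session that one arm has by design, and does not record whether controls received CtP. By itself it cannot determine whether another randomisation approach is needed. The control-arm count caps navigator-borne exposure, provided contacts are documented completely, and says nothing about self-use.

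The documents give no contamination rate, so no loss of power can be claimed for this trial. The fall from about 80% to about 62% at 20% exposure is an upper bound for that share. It rests on an assumed 0.6 SD effect (section 17.2 says only medium/large), 45 per arm and full benefit in exposed controls; partial benefit would cost less. The point deserves a change because it affects what the trial can tell the next one and existing records can improve the answer. It does not undermine the comparison of outcomes between arms.

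**What to change.** In section 5.1, with matching wording in 17.1:

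1. Base the decision on the number and proportion, with 95% CI, of controls with CtP exposure before their 6-month survey. Take this from ID-linked tool records and any CtP use written in navigator contact notes. The cut-off at the 6-month survey matters because controls may enter the waitlist extension, or be offered the link, after that survey. This assumes that records can be dated.
2. State in advance how the proportion and its interval will be read.
3. Report navigator contacts by arm with the protocol session excluded, and the share of controls with any navigator contact as the upper bound on navigator-borne exposure.
4. Declare as limitations untracked self-use of the online tool and guided use without an ID.
5. Label any dilution figures as upper bounds and give their assumptions.
6. If data collection is still open, and otherwise in the successor trial, add a yes/no field to the contact note for use of the CtP tool or its recommendations, and one 6-month survey item asked after the outcome measures so that it cannot colour those answers.

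Items 1 to 5 cost analysis wording and a record linkage. Item 6 adds a small burden for navigators and participants.

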7.0 Data Banking

N/A

8.0 Sharing of Results with Participants

8.1 Results are shared with participants after the conclusion of the study and once they are published prior to de-identification of our tracking files.

9.0 Study Duration

9.1

- In Phase I, caregivers of persons with ADRD will participate for about 1 month. In Phase II, caregivers of persons with ADRD will participate for about 6 months.
- We anticipate it will take 3 months to enroll 20 caregivers in Phase I, and approximately 8-10 months in Phase II.
- We anticipate completing all study procedures and data analysis in 24 months.

10.0 Study Population

10.1 Inclusion Criteria:

The care recipient has received a provider diagnosis of Alzheimer's disease or a related dementia (ADRD); and 2) the caregiver is 21 years of age or older; 3) English-speaking; 4) self-identifies as someone who provides help to the person with ADRD because of their cognitive impairments; 5) the caregiver indicates a willingness to use Care to Plan (CtP); and 6) caregiver resides in one of 4 Riverside Health regions (based on zip code). *Note: For study purposes, a diagnosis of mild cognitive impairment is considered along with related dementia diagnoses for study inclusion.*

10.2 Exclusion Criteria: Those who do not meet the inclusion criteria above are not eligible. Additionally, those who endorse a history of a serious mental health disorder whose: a) symptoms have exacerbated in the last six months, and b) are not receiving steady, ongoing pharmacological or other treatment for these symptoms, will be excluded from the project.

10.3 Screening:

To facilitate recruitment and enrollment in both phases of the project, RHS staff (e.g., RHS clinic management, social worker, Senior Care Navigator, or other staff) will present details about the CtP R21 study over the telephone. Those caregivers that express interest and agree to be contacted about the study are referred to the Riverside Senior Care Navigation project team, who securely share their contact information with the UMN research team ([name], the UMN research coordinator, and the research assistant). The inclusion criteria listed above will then be

PROTOCOL TITLE: Care to Plan: Preliminary Efficacy of a Tailored Resource for Family Members of Persons with Dementia

applied via a telephone-screening procedure by the UMN research coordinator or research assistant. Interested contacts that contact UMN staff directly will have the same screening and eligibility procedures applied. If eligible, the UMN research coordinator or research assistant will then describe the study process to an eligible caregiver, and proceed to the consent procedures.

11.0 Vulnerable Populations

11.1 Vulnerable Populations:

- Children
- Pregnant women/Fetuses/Neonates
- Prisoners
- Adults lacking capacity to consent and/or adults with diminished capacity to consent, including, but not limited to, those with acute medical conditions, psychiatric disorders, neurologic disorders, developmental disorders, and behavioral disorders
- Approached for participation in research during a stressful situation such as emergency room setting, childbirth (labor), etc.
- Disadvantaged in the distribution of social goods and services such as income, housing, or healthcare
- Serious health condition for which there are no satisfactory standard treatments
- Fear of negative consequences for not participating in the research (e.g. institutionalization, deportation, disclosure of stigmatizing behavior)
- Any other circumstance/dynamic that could increase vulnerability to coercion or exploitation that might influence consent to research or decision to continue in research
- Undervalued or disenfranchised social group
- Members of the military
- Non-English speakers
- Those unable to read (illiterate)
- Employees of the researcher
- Students of the researcher
- None of the above

Additional Safeguards:

Though not specifically targeted for inclusion, participants from some of the above groups may be allowed to participate. Due to the nature of the project and its risk, a specific capacity to consent assessment is not included. Participants will be reminded that all study procedures are voluntary and they can withdraw at any time. We do not anticipate any individuals from the above noted groups to have increased risk from participating in the proposed research, such as an increased risk of coercion,

PROTOCOL TITLE: Care to Plan: Preliminary Efficacy of a Tailored Resource for Family Members of Persons with Dementia

etc. Thus, our standard protocol practices (i.e. data security, confidentiality procedures, etc.) provide reasonable protections to these potentially vulnerable participants (including those listed above and any others who may meet inclusion criteria to enroll). Additionally, those who have had a serious mental health disorder whose: a) symptoms have exacerbated in the last six months, and b) are not receiving steady, ongoing pharmacological or other treatment for these symptoms, will be excluded from study participation.

12.0 Number of Participants

12.1 Number of Participants to be consented: In Phase I we plan to enroll 20 caregivers of persons with ADRD; for Phase II, we plan to enroll 100 caregivers of persons with ADRD. These numbers are the lowest that will allow for data analysis; it is possible that up to 25 caregivers in Phase I and 125 caregivers in Phase II may agree and consent to participant at most.

13.0 Recruitment Methods

13.1 Recruitment Process:

Riverside Health System (RHS) was selected as a site for the proposed R21 due to the ethnically, racially, and geographically diverse population of older adults served. The Senior Care Navigation case management program; a geriatric assessment clinic; a memory café program, an evidence based caregiver intervention program; and other RHS services will serve as sources of recruitment. Riverside staff (within and outside the project staff) may call/share information about the project via phone to their clients as desired (i.e. when waiting for appointments, etc.). Interested contacts will have their contact information securely transferred to study staff. Other sources of recruitment may include Riverside Center for Excellence in Aging and Lifelong Health outreach; radio interviews; community organizations and events; Riverside or community leadership; letters to providers to share information about the study; the Riverside Intranet; newspaper advertisements; and other IRB-approved flyers (electronic/hard copy), print ads, e-mail, newsletters, and social media (i.e. Instagram, Facebook, Twitter, LinkedIn, etc.) ads. Registration forms for educational presentations (by study staff or other agencies) may include an opportunity for individuals interested to provide their permission for the research team to contact them to share additional information about the study. *[Thus, by nature of this, UMN staff or other agency staff involved in planning, hosting, or post-webinar certificates will have access to the names/contact information of those indicating interest in receiving more information about the study].* Presentation “polls” may offer an additional opportunity for presentation attendees to provide permission for contact. Presentation slides may also be used during these community presentations to increase outreach. Hard copy permission forms may also be presented at in-person presentations. Ads/approved presentation slides may also be displayed online/electronically via

PROTOCOL TITLE: Care to Plan: Preliminary Efficacy of a Tailored Resource for Family Members of Persons with Dementia

television in clinics/waiting rooms throughout Riverside or other organizations, or as visual television ad in community. IRB approved recruitment ads/text may be used for recruitment via other protocol-approved modalities (i.e. approved newspaper ad used within emails, etc.). *Note: General promotional materials/text (emails/newsletters/flyers/etc) are shared in the context of general promotional recruitment efforts. However, study staff do not pursue individualized study-related contact with potential participants until contact is made by an interested individual or a permission form/request for information is obtained.*

From January 2017 to May 2018 a total of 2,123 individuals were served. Approximately 63% (n = 1,330) were women. Close to 70% (n = 1,430) had cognitive impairment. Twenty percent of clients served were from rural areas (n = 425) and over 30% were African-American (n = 658). A little over 5% of all clients served over the 17 month period were Hispanic/Latino (n = 116).

To facilitate recruitment and enrollment in both phases of the project, RHS staff (e.g., RHS clinic management, social worker, Senior Care Navigator, or other staff) will present details about the CtP R21 study over the telephone. Those caregivers that express interest and agree to be contacted about the study are referred to Riverside Senior Care Navigation project team, who securely share their contact information with the UMN research team ([name], the UMN research coordinator, and research assistant). For interested individuals that may contact the UMN team directly, the same screening and eligibility procedures will be applied.

13.2 Recruitment Materials:

To facilitate CtP recruitment, a flyer will be utilized and developed. Prior to use, all flyers and ads will be IRB-approved.

13.3 Payment:

All caregivers in the proposed project will also be provided with up to \$100 incentive upon study completion. Greenphire ClinCard will be used for compensation; we include the template language in the consent form.

For phase I, participants must complete the initial survey, review the Care to Plan tool during the month after enrollment, and complete the one month follow up survey and interview via phone with the University of Minnesota research team in order to receive this \$100 compensation. A prorated payment of \$75 will be given to those who wish to opt out of the semi-structured interview.

For phase II, participants are eligible to receive the study compensation based on completion of the initial survey, 3 and 6 month follow up, as well as the

PROTOCOL TITLE: Care to Plan: Preliminary Efficacy of a Tailored Resource for Family Members of Persons with Dementia

telephone interview with the University of Minnesota research team (if selected). Participants will be paid \$25 for each survey time-point (up to \$75), and an additional \$25 (for a total up to \$100) if selected for a final telephone interview. When necessary or unable to complete a survey in full, participants will be fully compensated for partially completed surveys.

13.4 Withdrawal Circumstances:

We do not anticipate encountering circumstances under which participants will be withdrawn from the research without their consent. The only instance is if the caregiver reports they have engaged in self-harm or have harmed the care recipient with dementia; in such instances, the appropriate authority in Virginia (Adult Protective Services in Virginia; [contact]; see <http://www.dss.virginia.gov/family/as/aps.cgi>) will be notified. Additionally, if the study staff have reason to believe that the intervention is causing the participant harm, or the participant is deliberately jeopardizing the integrity of the study, the participant may be withdrawn at the PI's discretion.

During phase I, participants who do not complete Care to Plan in the 1-month timeframe following their baseline survey will be considered lost to follow up, and the 1 month checklist and interview will not be administered. During phase II, participants that do not complete Care to Plan within the first 3 months following their baseline survey will continue follow up surveys at 3 and 6-month time-points, but would not be administered a 21-item checklist or telephone interview.

13.5 Withdrawal Procedures: If caregivers withdraw from the study, we will not conduct additional data from them.

13.6 Termination Procedures: Data prior to termination/withdrawal will be utilized in subsequent analyses.

